Perceived spousal support (SS): The Family Management Measure¹⁴⁸ assesses how families manage caring for children with chronic conditions like T1D. We will use the 8-item Parental Mutuality scale that measures parents' perceptions of support, shared views, and satisfaction with how the partners work together to manage the child's condition. The scale will be completed only by parents living with adult partners. The scale has adequate internal consistency ($\alpha=0.73$ for mothers, $\alpha=0.77$ for fathers), inter-rater reliability ($r=0.44$), and test-retest reliability ($r=.71$), and correlations in the expected direction with measures of related constructs.

Eyberg Childhood Behavior Inventory (ECBI) (ICC): The ECBI¹⁶¹ is a widely used parent-report measure of problematic behaviors of children ≥ 2 years old. Parents rate the frequency of 36 child behaviors on a Likert scale, that ranges from 1 (*never*) to 7 (*always*), and to then indicate whether they consider each behavior to be a problem (yes/no). The ECBI has strong reliability and validity.¹⁶² The ECBI will be administered at Baseline only to provide a comparator for evaluation of the convergent validity of the Preschool Diabetes behavior Checklist described below.

Diabetes-specific routines (BC): The Pediatric Diabetes Routines Questionnaire (PDRQ)³⁷ measures the frequency of routines formed around managing diabetes in the family. Item frequency is measured on a 5-point Likert scale ranging from 0 “never” to 4 “everyday” and “not applicable.” Internal consistency ($\alpha=0.88$) and test-retest reliability ($r=0.81$) estimates were strong. Construct validity was supported through relations with general child routines, family rituals, diabetes treatment adherence, and diabetes-specific family support. Completion of the PDRQ at the Baseline evaluation only will permit evaluation of the scale's predictive validity.

Measures obtained at Baseline, 6 months, and 12 months:

Parent self-efficacy (IPC): The Parental Self-Efficacy Scale for Diabetes Management (PSESDM)¹⁵³ was adapted from a prior measure for adult patients to measure parental self-efficacy for diabetes management of young children. The 8-item scale has adequate internal consistency ($\alpha=0.84$). Criterion validity was established. Higher scores were associated with more favorable HbA1c and quality of life in children.

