Family Management Measure: Parent Mutuality Scale	•		
Parenting Self-Efficacy Scale for Diabetes Management	•	•	•
Brief Symptom Inventory-18	•	•	•
Parent-Preschooler Diabetes Adjustment Scale	•	•	•
Benefit Finding Scale	•	•	•
Hypoglycemia Fear Survey-Parents of Young Children version	•	•	•
Preschool Diabetes Behavior Checklist-Revised	•	•	•
Eyberg Child Behavior Inventory	•		
Diabetes Self-Management Profile-Self Report Form	•	•	•
Pediatric Diabetes Routines Questionnaire	•		
Mid-RCT and Post-RCT Qualitative interview (Website group @ 3, 6 &12 months)	•	•	•

RCT Analytic Plans: The RCT analysis plan aligns with the focus of PA-DK-14-022, i.e., to develop an intervention that is ready for testing in a rigorous, multisite RCT. Because this is conceived as a preliminary RCT, we have put forth hypotheses below, but the plan emphasizes deriving effect size estimates for powering future trials on the main efficacy endpoints and analysis of website use and benefit. The planned RCT sample size of 150 families (2:1 for Website: UC) will suffice to estimate efficacy and to derive effect size estimates for use in a future trial with formal hypothesis testing.

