Fundamentals: The Full Analysis Set will include parents who contribute data at either 6 or 12 mos.¹⁶⁷⁻¹⁶⁹ The Completer Analysis set will include those who provide data at 0, 6 and 12 mos..¹⁶⁷⁻¹⁶⁹ Efficacy analyses will be done on both sets.¹⁶⁷⁻¹⁶⁹ The statistician will make appropriate analytic adjustments for instances in which data are determined to be Missing at Random and Missing Completely at Random.¹⁶⁷⁻¹⁶⁹ In addition to multiple imputation, sensitivity analyses will be performed for assessing the robustness of the estimation in case of Missing Not At Random. Descriptive statistics will be calculated for all measures and distributions of obtained data will be summarized graphically in aggregate and by group. Assumptions for all proposed models will be checked before statistical analyses.¹⁶⁷⁻¹⁷¹ Appropriate transformations or non-parametric methods will be used in cases of violated model assumptions.¹⁶⁷⁻¹⁷¹ Sensitivity analyses will be conducted when assumptions underlying specific analyses cannot be verified using actual study data. Psychometric properties of all questionnaires will be calculated based on this sample's results, including internal consistency, 6 and 12-month test-retest reliability and predictive validity. All tests will be performed against a two-sided alternative at the $\alpha= 0.05$ significance level and a 95% confidence interval or a p-value will be provided for inferential purposes. All analyses will be performed using the most recent version of the SAS statistical software package.¹⁷² One way ANOVA of continuous baseline variables and a Fisher exact test/chi-square test/CMH test for categorical variables will be used to compare Website and UC at baseline.¹⁶⁷⁻¹⁷¹ Analyses of primary and secondary end points will be adjusted for imbalanced baseline characteristics.

Primary Analyses: Linear mixed effects modeling will be the primary analytic approach.¹⁷²⁻¹⁷⁷ Holmbeck's¹⁷⁸ methods will be used to evaluate moderation and mediation of treatment effects. Candidate moderators will include demographic variables and scores for each measure obtained at baseline. Candidate mediators will include scores on each questionnaire obtained at 0, 6 and 12 months. With three measurement points, these methods will be capable of detecting linear and quadratic longitudinal associations among study variables. We will test these primary hypotheses:

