H1: Compared to UC participants, Website participants will have significantly more favorable status at 6 and 12 months on HbA1c (primary outcome) and secondary outcomes consisting of change in questionnaire scores at follow-up visits.

H2: Website treatment effects will be moderated by parental socioeconomic status and questionnaire scores at baseline visits

H3: Website treatment effects will be mediated by changes in change in questionnaire scores at follow-up visits.

H4: Among Website participants, the above treatment effects will be mediated by Website utilization (More utilization predictive of more beneficial effects).

Perhaps more importantly, this feasibility trial will yield rich data that will be used for estimation of effect sizes and sample size requirements for a future multi-center trial,¹⁷⁹⁻¹⁸⁰ and will enhance that application by:

1. Estimating Website-UC effect sizes (Cohen's *d* index)¹⁷⁹⁻¹⁸¹ at 6 and 12 months on the primary and secondary outcome variables.
2. Exploring utilization of the online resource, by examining demographic variables and individual characteristics of parents and children as moderators of Website use, and change in time-varying variables as mediators of change in Website use over 6 and 12 mo.¹⁷³⁻¹⁷⁸
3. Use of Structural Equation Modeling to evaluate and refine the conceptual model put forth earlier.¹⁸¹
4. Analyzing Mid-RCT and Post-RCT qualitative interviews of participants will provide additional information to drive refinements in the WEBSITE for future trials that could enhance WEBSITE use and benefit.

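### H1, listed as a primary hypothesis, claims significance on seven unadjusted questionnaires at two visits, which conflicts with the plan's own estimation framing

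*Combined protocol and SAP*

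**What the plan says.** All of this is in section 4.2 unless noted.

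- **Status of H1.** Primary Analyses introduces H1 to H4 with "We will test these primary hypotheses".
- **Content of H1.** It predicts that "Website participants will have significantly more favorable status at 6 and 12 months on HbA1c (primary outcome"), and then adds "secondary outcomes consisting of change in questionnaire scores at follow-up visits". The questionnaires are neither named nor ranked there.
- **Error rate.** Fundamentals states one rule: "All tests will be performed against a two-sided alternative at the" 0.05 level, with a confidence interval or a p-value given for inference.
- **Which questionnaires.** Under "Measures obtained at Baseline, 6 months, and 12 months" and in Table 1, seven are repeated: the parental self-efficacy scale, BSI-18, PP-DAS, Benefit Finding, HFS-PYC, PDBC and DSMP-SR.
- **Primary and secondary.** Study design names 6-month change in HbA1c as the primary outcome. H1 also marks HbA1c as primary and the questionnaires as secondary.
- **Estimation framing.** RCT Analytic Plans says the sample suffices to estimate efficacy and to "derive effect size estimates for use in a future trial with formal hypothesis testing". Aim 3 (section 2) speaks of exploring treatment effects. The list after H4 commits to Cohen's d at 6 and 12 months on primary and secondary outcomes.
- **What is absent.** There is no multiplicity adjustment, testing order, key secondary outcome or gate on HbA1c.

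**The concern.** The plan gives two accounts of the questionnaire results. In one, they are estimates to inform a later trial, where formal testing belongs. In the other, they are part of a primary hypothesis, stated as significance claims at an unadjusted 0.05 at each of two visits. H1 does not say whether all of its components must be met or whether one is enough.

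An author who follows Primary Analyses literally could offer one questionnaire with p<0.05 at one visit as support for a primary hypothesis, even with a null HbA1c result. Two things are at stake. A chance finding could be reported as efficacy. A scale picked for the multisite trial because it crossed 0.05 would also bring an inflated effect size into the sample-size calculation this trial is meant to supply.

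**Working it through.** The plan states no family-wise error rate, so there is no figure of its own to reproduce.

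**Inputs from the documents**
- Two-sided 0.05 per test (Fundamentals). In the direction of benefit that is 0.025.
- Seven repeated questionnaires (Table 1) and two follow-up visits (H1): 7 × 2 = 14 tests on total scores. The model contrasts are not specified, so 7 (one test per scale) is the lower count.
- 150 families at 2:1 (RCT Analytic Plans), that is 100:50.

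**Assumption.** The documents give no correlation between scales or visits. I take a common correlation ρ of 0.5, with a range from 0 to 0.7.

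**Formula.** With no website effect and k equally correlated z-tests, and c = 1.96:
- at least one false benefit: 1 − ∫ Φ((c − √ρ·u)/√(1−ρ))^k φ(u) du
- at least one false result in either direction: the same, with Φ(·) replaced by the probability of lying between −c and c given u.

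At ρ = 0 these reduce to 1 − 0.975^k and 1 − 0.95^k. For k = 7: 1 − 0.975^7 = 0.162 and 1 − 0.95^7 = 0.302. For k = 14: 0.298 and 0.512.

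| k | ρ | False benefit | Either direction |
|---|---|---|---|
| 7 | 0 | 0.162 | 0.302 |
| 7 | 0.3 | 0.137 | 0.271 |
| 7 | 0.5 | 0.115 | 0.230 |
| 7 | 0.7 | 0.089 | 0.178 |
| 14 | 0 | 0.298 | 0.512 |
| 14 | 0.3 | 0.224 | 0.438 |
| 14 | 0.5 | 0.174 | 0.348 |
| 14 | 0.7 | 0.124 | 0.249 |

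**Check with a less uniform structure.** I simulated 7 scales × 2 visits with correlation 0.3 to 0.7 between scales and 0.5 to 0.7 between visits (400,000 draws). The false-benefit rate was 0.14 to 0.23, and the either-direction rate 0.28 to 0.44.

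**If more scores were tested**
- Adding the two HFS-PYC and three BSI-18 subscales gives 12 scores and 24 tests. The false-benefit rate is 0.26 to 0.33, with correlation 0.3 to 0.5 between scores and 0.5 between visits. The plan does not say that subscales will be tested.
- The Eyberg inventory is baseline-only in Table 1 but is described as repeated under Adequacy of protections against risks. If repeated, there are 16 tests, and the false-benefit rate under independence is 1 − 0.975^16 = 0.333.

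**Selected effect sizes.** At 100:50 the standard error of d is about √(1/100 + 1/50) = 0.173. A scale must show d of about 1.96 × 0.173 = 0.34 to reach p<0.05, so a null scale that crosses the line enters the next trial's planning at 0.34 or more.

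**Cost of adjusting.** Detectable d with 80% power, at 100:50 with no dropout:
- unadjusted: (1.960 + 0.842) × 0.173 = 0.485
- strictest Holm step over seven, alpha 0.05/7 = 0.0071: (2.690 + 0.842) × 0.173 = 0.612.

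**The case against.** The strongest reply is that the plan already treats these outcomes as secondary in a preliminary trial. HbA1c is the single primary outcome, Aim 3 speaks of exploring effects, formal testing is left to a later trial, and Cohen's d is already promised for every outcome. That stands in part: the plan does separate primary from secondary and does have an exploratory framing. It does not carry that framing to where the tests are specified. H1 still lists the questionnaires under primary hypotheses, with a significance claim and no order among them.

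A second reply is that H1 joins its outcomes with an *and*, and nowhere says one questionnaire is enough. This also stands. If every outcome had to be significant, the error rate would be near zero. The inflation depends on an any-one-suffices reading, which the text neither states nor excludes.

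A third is that 14 is not a fixed count, because the mixed-model contrasts are not specified. That is why the results are shown for 7 as well.

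A reader might infer that a false benefit is likely. The figures do not support that. Rates that reach one half on total scores count false harm as well, which cannot support H1, and they need near-independence between scales answered by the same parent.

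**Conclusion.** The concern holds as a conflict of wording with a measurable consequence. If the website has no effect and any one significant total score is read as support, the chance of at least one false benefit is about 0.115 at one visit (0.09 to 0.16) and about 0.17 over two visits (0.12 to 0.30). One test would carry 0.025, so the inflation is roughly 3.6-fold (0.089/0.025) to 12-fold (0.298/0.025). Counting either direction, the rates are 0.18 to 0.30 and 0.25 to 0.51, against 0.05. All of these rest on assumed correlations from 0.7 to 0, since the documents give none.

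The HbA1c test is not affected by this. The point bears on how questionnaire results are reported and carried forward. It should be settled before analysis but does not threaten the trial's primary comparison.

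**What to change.** In Primary Analyses:

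1. Limit H1 to HbA1c.
2. Name the seven questionnaire total scores as exploratory secondary outcomes. Report each as a Website-UC difference and Cohen's d (already planned) with a 95% CI, without a significance claim.
3. If any questionnaire result is to be called significant, require Holm adjustment across a family stated in advance: for example the seven month-6 totals, or all 14 if month 12 is also claimed. Month 6 is the cleaner choice, because Usual Care parents are invited to use the website after the first 6 months. Multiplicity control alone does not require it.

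The cost is wording and the loss of unadjusted significance claims on questionnaires; no data or sample size changes. If Holm over seven is used, the d detectable with 80% power at the strictest step rises from about 0.49 to 0.61, assuming 100:50 and no dropout. With the 225 children projected under Inclusion of Children (150:75, standard error √(1/150 + 1/75) = 0.141), it would rise from about 0.40 to 0.50.

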PHASE 2: Randomized, Controlled Trial of the Effects of 12 Months' Use of an Online Resource for Parents of Very Young Children with Type 1 Diabetes Once the online resource is nearly ready to accept users, the randomized controlled trial protocol will be submitted for review and approval by Nemours IRB #1. The study would be an interventional study that appears to pose no more than minimal risks to participants. All of the participants will be adult parents/legal caregivers of children with type 1 diabetes under the age of 6 years at enrollment. The researchers will not interact directly with the children, but they will be considered secondary participants in this research since the intervention is designed to promote their health, safety and well-being.

Human participants' involvement, characteristics and design: We seek to enroll parents or other legal caregivers of eligible children receiving T1D care at any operating entity of Nemours Children's Health System or elsewhere in the United States if enrolled via online recruitment. We estimate that we can easily enroll a sample of up to 300 families when this RCT is opened to enrollment. While parents are the primary participants and will all be adults at the time of enrollment, their young children with T1D are secondary participants since their behavior and health outcomes are measured in the study. Participants will include adult parents/caregivers who self-identify as parents/caregivers of up to 300 children who were diagnosed with T1D before the age of 6 years, whose children carry a physician diagnosis of T1D and receive care at any Nemours Children's Health System location in the Delaware Valley or Florida, (or elsewhere in the United States if recruited online), and whose children are not yet 6 years old at the time of enrollment. We have estimated that 225 mothers and 75 fathers will provide consent to participate, but would be delighted to enroll every father of every eligible child. The study design will be a 2X3 randomized treatments design with 2 groups (Website and Usual Care; UC) and 3 measurement points (0, 6 and 12 months). Families (mother-father dyads and their children with T1D) will be randomized, stratified by insulin modality (pump or injections) and recruitment method (Nemours or online enrollment), in a 2:1 (Website:UC) ratio to optimize how much can be learned about moderation and mediation of SMP effects and to elucidate SMP utilization and its correlates. All children will receive T1D care at a Nemours diabetes center in Florida or the Delaware Valley, or elsewhere in the United States if enrolled online.. Children enrolled in this trial will receive T1D care that is equivalent to what similar children not enrolled in the study would receive at the same centers.

Informed Consent Process: Using IRB-approved, electronic informed consent infrastructure established in ongoing research at Nemours by [name] (1-R01HL114899-01: Use of Mobile Devices and the Internet to Streamline an Asthma Clinical Trial), parents will electronically authenticate an IRB-approved informed consent form that will include all of the federally required elements of informed consent and that fulfills Nemours pertinent policies and procedures. Per Nemours policy, assent is not required for children under 7 years of age to participate in research if appropriate parental permission has been obtained, as it will be in this case.

Sources of research data This study will involve parental completion of questionnaires at baseline, 6 and 12 months and either 1. For parents of Nemours patients, access to the child's electronic health record for retrieval of recent HbA1c results and documentation of symptomatic and severe hypoglycemic episodes or 2.).

For parents recruited online, parents will collect and submit dried blood spots. Parents' use of the online resource will also be tracked automatically. At 3, 6 and 12 months after randomization or upon withdrawing the study, parents randomized to Website Access will be asked to complete a qualitative interview about their experiences with use of the website and their suggested refinements.

Potential risks: The most likely risks are privacy threats and possible loss of confidentiality, but it would be difficult to characterize the potential for harm to participants since the questions do not address illegal, unethical or stigmatizing behaviors and all of the participants are adults who may simply decline to answer any question that is perceived to be threatening. Participants randomized to UC may be at somewhat higher risk of deterioration in metabolic, behavioral and affective outcomes than those randomized to SMP. There is little reason to believe that parent or child participants will fare more poorly due to study involvement than if they had not enrolled.

Parents in this phase of the research will be completing the Brief Symptom Inventory, a psychiatric symptom screening measure, and the Eyberg Child Behavior Inventory, a screening measure of childhood behavioral problems, at 0, 6 and 12 months, affording an opportunity to detect clinically significant symptom levels as well as deterioration in psychiatric status at each measurement point. Parents whose scores exceed a clinical cutoff of T-score ≥ 65 on the Brief Symptom Inventory, or whose children score above the Eyberg Child Behavior Inventory clinical cutoff scores of 127 for Intensity or 11 for Number of Problems, will be contacted by telephone as soon as possible after the elevated score is obtained and assisted by the research team in obtaining a referral to a psychologist, psychiatrist or qualified mental health service provider in their region for further evaluation and possible treatment.

Special attention will be given to monitoring of deterioration in diabetes outcomes among UC participants. All Nemours sites include multidisciplinary resources to which patients can be referred for augmented care and education in nursing, nutrition, psychology, and social work should the child's health status or psychological adjustment require such actions.

Potential benefits to participants and others: Participants in the Website group may benefit in a variety of ways from use of the online resource, but this cannot be guaranteed. Participants may appreciate the opportunity to help others who face the challenges of living with T1D in this age group.

Importance of the knowledge to be gained: The study will yield extensive information from parents for parents about the content, structure, function and governance of a social media portal for parents of very young children with type 1 diabetes. There is no other study that has compiled this kind of information from parents for this specific purpose. Nor has any study returned to the same parents to ensure that their perspectives have been reflected appropriately in the subsequent stage of refined website design and execution.

Data and safety monitoring plan: The study poses no greater than minimal risk but it does involve a clinical trial of a behavioral intervention. In our opinions, the level of risk that is likely to be encountered by participants in this study does not rise to the level that requires an independent or external DSMB. Instead, Drs. [name], [name] and [name] will serve as safety officers who will oversee participants' experiences, receive any unanticipated problem reports or participant complaints, ensure IRB notification as required by Nemours policies and procedures, and implement indicated safety precautions or other human subjects protection actions. Special attention will be given to monitoring of deterioration in diabetes outcomes among UC participants.

REPRESENTATION OF FEMALES, MINORITIES AND CHILDREN

Inclusion of Females

Females are expected to represent a majority of parent-participants in both the Social Media Portal Design and Development Phase (~76%) and the Randomized Controlled Trial (~67%). Females absorb the bulk of responsibility for T1D care for children under 6 and we expect that they may be more frequent users of the social media portal once it is completed.

Female children will represent about half of the child participants in the Randomized Controlled Trial.

Inclusion of Minorities

There is little direct scientific evidence indicating that racial or ethnic minority status, economic disadvantage or low health literacy/numeracy are associated differentially with benefit accrued from using a social media portal such as that proposed here. However, given the robust nature of health care disparities in other contexts, it is reasonable to suspect that these groups may derive less benefit from this resource than other, more advantaged, demographic groups. We have therefore designed the research plan to enable evaluation of these questions and to give disadvantaged populations equitable access to the potential benefits of participation in this research. In addition to oversampling of racial and ethnic minorities, we will strive to achieve exceptional diversity in our enrolled samples in terms of household income, education, health literacy/numeracy and internet and social media fluency

In the randomized controlled trial, we expect to enroll 84 parents (28% of the sample) who are members of racial minority groups, including African Americans (11%), Asians (9%) and Multiple/Other (11%). In terms of ethnicity, Hispanics will account for about 7% of the participants in the RCT.

Inclusion of Children

We project that 300 parents (225 "mothers" and "75 fathers") of 225 distinct children with T1D will enroll in the study. In the randomized controlled trial, these 225 children will be secondary participants in that parents will complete questionnaires about them and routinely obtained clinical data will be retrieved from their electronic medical records. We expect their racial and ethnic composition to parallel that of their parents (about 28% racial minorities and about 7% of Hispanic ethnicity). Recruitment of racial and ethnic minorities is limited in this trial by the racial and ethnic composition of the available clinical population.. We will strive to enroll every family of every eligible child, but we estimate that parents/caregivers of about 225 children with T1D will actually enroll.

Multiple PI Leadership Plan

[name], ABPP and [name] will serve as Multiple Principal Investigators on this grant. Our rationale for organizing the application in this way rests on these considerations:

- [name] has a very strong track record of obtaining external funding for his program of research on family adaptation to pediatric T1D and in the implementation, management, analysis and dissemination of that research. He also has an extensive background in human subjects protection and the responsible conduct of research.
- [name] has multiple commitments that prevent him from dedicating more than 20% of his time and effort to this work. Providing opportunities for [name] to learn the grant submission and management process offers a serendipitous way for him to pursue this innovative and exciting work at a somewhat lower level of effort that he can deliver with certainty.
- [name] is an emerging investigator who brings special qualifications to the project, in that she was diagnosed with type 1 diabetes at an early age and she is exceptionally familiar with the diabetes online community.
- [name] is experienced in website design and development based on stakeholder-driven design and construction of two web platforms for decision aids in his ongoing PCORI-funded study.

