Measurement Strategy: The measurement plan aligns directly with the conceptual model. Little is known about variables that might influence and be influenced by parent use of the planned website, so the measurement plan for this trial is broad in scope. This will magnify participation burden, but the collection of a thorough assessment of model constructs will best facilitate planning a future, larger trial, to evaluate the model in its entirety and to determine if parent or child characteristics moderate or mediate website benefits. Hence, parents will be paid for completing scheduled measures on an escalating basis: Baseline \$25; 6 months: \$50 and 12 months: \$75. Questionnaires will be completed online using existing REDCap capabilities. T1D-specific measures were reviewed by the Family Advisors and adapted for the YC-T1D population. The conceptual model constructs associated with each measure are denoted as follows: Social Support (SS), Individual Parent Characteristics (IPC), Affective Coping (AC), Behavioral Coping (BC), Individual Child Characteristics (ICC), T1D Management Behaviors (DMB), Hypoglycemia (H), Glycated hemoglobin (A1C), and Quality of Life (QOL). Certain measures, as described in the Human Subjects section, yield clinical cutoff scores. Parents or children whose scores on those measures exceed a clinical cutoff will be contacted promptly and assisted in arranging an appointment with a qualified mental health professional in their areas. The Eyberg Child Behavior Inventory and the Brief Symptom Inventory-18 are commercially available. Per communication with the publishers (PAR and Pearson, respectively; see Appendix A), we have received approval pending completion of license/fee agreements to administer these measures online via REDCap.

Measures obtained at Baseline only:

Demographic information (IPC and ICC): The same demographic form used in the Website Design and Development Phase will be collected from RCT participants at baseline.

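### The safety section has the Eyberg inventory completed at 0, 6 and 12 months, but the measurement plan and Table 1 schedule it at baseline only

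*Combined protocol and SAP*

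**What the plan says.** The Human Subjects Protection section, under Adequacy of protections against risks, describes a screening safeguard for the randomized trial. Parents are to complete the Brief Symptom Inventory "and the Eyberg Child Behavior Inventory, a screening measure of childhood behavioral problems, at 0, 6 and 12 months". The purpose of this repeated schedule is given in the same sentence, which describes it as "affording an opportunity to detect clinically significant symptom levels as well as deterioration in psychiatric status at each measurement point". The paragraph then sets the Eyberg trigger at "clinical cutoff scores of 127 for Intensity or 11 for Number of Problems". A child scoring above either value leads to a telephone call and help in finding a mental health provider in the family's region.

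Section 4.2, Measurement Strategy, relies on that text for its cutoff rule: "Certain measures, as described in the Human Subjects section, yield clinical cutoff scores". It then places the Eyberg under the heading "Measures obtained at Baseline only". The description of the scale repeats this and gives a reason: "The ECBI will be administered at Baseline only to provide a comparator for evaluation of the convergent validity". The scale to be validated in this way is the Preschool Diabetes Behavior Checklist. The Eyberg row of Table 1 has one mark, at baseline. The Brief Symptom Inventory-18 row has marks at all three visits.

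**The concern.** The two parts of the document give different schedules for the same instrument, and one of them describes a participant protection. Staff who work from section 4.2 and Table 1 will not collect the Eyberg at 6 and 12 months. The child screen that the Human Subjects section describes at those visits then does not take place.

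This is an internal inconsistency. Neither schedule is being criticised as a design. The choice does carry an analytic consequence. Hypothesis H1 takes changes in questionnaire scores at follow-up as secondary outcomes, and the candidate mediators are the questionnaires collected at all three visits. An Eyberg given three times fits both descriptions; one given only at baseline fits neither.

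**Working it through.** No sample-size or power figure is involved. The check compares the texts and counts.

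**The schedules side by side**

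| Place | Eyberg | Brief Symptom Inventory-18 |
|---|---|---|
| Human Subjects Protection, Adequacy of protections against risks | 0, 6, 12 months | 0, 6, 12 months |
| Section 4.2, heading above the scale | Baseline only | 0, 6, 12 months |
| Section 4.2, Table 1 | Baseline | 0, 6, 12 months |

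The Eyberg description in section 4.2 also says baseline only.

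**Could this be a table-reading fault?** Unlikely. The running text of section 4.2 agrees with the single mark in Table 1, and the Brief Symptom Inventory-18 agrees in all three places. Neither Eyberg statement comes from a change log.

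**Screens lost under the measurement plan**

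- Eyberg administrations: 3 in the safety text, 1 in the measurement plan; 3 − 1 = 2 absent.
- Changes from baseline that can be observed with one administration: 0 of 2.
- Scales with a stated cutoff: 2 at baseline (Brief Symptom Inventory-18 for the parent, Eyberg for the child); 1 at 6 and at 12 months (Brief Symptom Inventory-18).
- Child scales with a stated cutoff after baseline: 0. The Preschool Diabetes Behavior Checklist is repeated at every visit, but no cutoff is given for it.

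**What remains in place.** The trigger sentence names no visit, so it operates whenever an Eyberg is collected. Under the measurement plan that means baseline. The parent screen, monitoring by the child's own health care team and the safety officers are unaffected. One further safeguard is described only for some participants: "All Nemours sites include multidisciplinary resources to which patients can be referred". Section 4.2 projects up to 120 Nemours patients and the section on inclusion of children projects 225 children, so on those figures at least 225 − 120 = 105 children would be enrolled elsewhere. With the plan's other totals the figure is at least 150 − 120 = 30 (150 families), or 300 − 120 = 180 if the maximum of 300 families is reached.

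**What a three-visit Eyberg would add**

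- Questionnaires marked at all three visits in Table 1: self-efficacy, Brief Symptom Inventory-18, Parent-Preschooler Diabetes Adjustment Scale, Benefit Finding, Hypoglycemia Fear Survey, Preschool Diabetes Behavior Checklist, Diabetes Self-Management Profile = 7. With the Eyberg, 7 + 1 = 8.
- Change scores: 2 scores (Intensity, Number of Problems) × 2 follow-up visits = up to 4.
- Burden: "Parents rate the frequency of 36 child behaviors on a Likert scale", and they also mark each as a problem or not. That gives 36 items × 2 responses × 2 visits = up to 144 further responses per parent.

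**The case against.** The strongest reply is that little hangs on this. The document describes the trial as minimal risk, health care teams monitor all patients and parents, and the parent screen is intact. The contact rule is tied to no visit, so it works wherever the scale is given. The mention of deterioration in psychiatric status may also refer only to the parent scale. On this view the safety paragraph needs a one-sentence correction.

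Much of that is fair, and it limits the consequence. It does not remove the contradiction: the 0, 6 and 12 month schedule names both scales in one sentence, whichever of them the deterioration clause refers to.

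Three smaller points also stand:

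- Section 4.2 describes the Eyberg as a measure for children aged 2 or older, while the trial enrolls children under 6 with no lower age limit. The counts above therefore do not apply equally to every child, and the baseline screen is itself qualified for the youngest.
- The generic wording of H1 and of the candidate mediators would already take in a three-visit Eyberg. A sentence on its role is good practice; its absence is not a second contradiction.
- No cutoff is promised anywhere for the Preschool Diabetes Behavior Checklist, so the absence of one is context and not a fault.

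**Conclusion.** The concern holds. The document gives two incompatible schedules for the Eyberg, three administrations against one, and nothing elsewhere resolves them. If the measurement plan is followed, two of the three child screens described as a participant protection do not happen, and no child scale with a stated cutoff is left after baseline. This assumes that staff work from section 4.2 and Table 1; the documents do not show what was built into the online data system.

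The effect is limited to the Eyberg screen after baseline. The primary HbA1c comparison is untouched, and the baseline Eyberg is a candidate moderator under either schedule. The point should be corrected, but it does not threaten the trial's main result.

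**What to change.** Bring section 4.2 (the heading, the Eyberg description and Table 1) and the Human Subjects Protection section to a single Eyberg schedule. The documents do not show which is intended, so the sponsor must decide. There are two routes:

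- **Limit the safety text.** State that Eyberg screening takes place at baseline, keep 0, 6 and 12 months for the Brief Symptom Inventory-18, and make clear that detection of deterioration rests on the latter. This costs wording only.
- **Extend the measurement plan.** Show the Eyberg at 0, 6 and 12 months in section 4.2 and Table 1. This adds the 36-item form at two visits, up to 144 responses per parent, under the license and fee agreement that section 4.2 already mentions. RCT Analytic Plans should then say whether the Eyberg change scores join the H1 secondary outcomes and the candidate mediators.
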